Sub-analyses of the endpoints will be performed across subject cohorts (i.e., PCI, CABG and medical management). Comparisons for primary and secondary endpoints will be done for PZ-128 in aggregate and per dosing group. The potential influence of baseline risk factors and concomitant therapies such as statins, choice of P2Y₁₂, and aspirin dosing on the incidences of the endpoints will also be explored using generalized linear models and survival models.

[figure not shown]
Subgroup analyses will be conducted for baseline characteristic variables such as age, sex, and race. All bleeding events will be characterized as non-CABG or CABG related and the following bleeding rates will be reported: total, CABG-related and non-CABG-related.

Tabulations of descriptive statistics will be provided for TIMI major plus minor bleeding. In addition, tabulations of descriptive statistics will also be provided on the incidence of all other relevant variables.

Although no formal stopping boundaries will be utilized, one interim safety analysis will be performed at approximately one year following the enrollment of the first subject, or after enrollment of 50% of the study population, whichever occurs first. The Data and Safety Monitoring Board (DSMB) will be provided point and interval estimates of PZ-128 benefit at the time of that analysis based on survival estimates, and will evaluate evidence of bleeding risk in light of the potential efficacy benefits in making recommendations about stopping the trial.

Among the committees formed to oversee the conduct of the study will be an independent DSMB to protect further the rights, safety and well-being of subjects who will be participating in this study by monitoring the progress and results of the trial, and an independent Clinical Events Committee (CEC) to review and adjudicate each suspected bleeding and efficacy endpoint event while blinded to treatment.

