All subjects will complete the protocol-specified in-hospital tests, collections, and evaluations up to the time they are discharged from the hospital. The duration of hospitalization will vary depending upon the clinical circumstances (e.g., subject comorbidities, type of procedure(s), complications from procedure(s), and need for further testing /procedures) and local standards

of care and may include same day discharge, overnight stay for observation or inpatient admission.

Prior to discharge from the hospital, the return visit will be scheduled for 14 days (± 5 d) after the administration of the study drug, and follow-up telephone contacts should be scheduled for 30 days (± 5 d) and 90 days (± 7 d) after the administration of the study drug.

Appropriate assessments will be used to characterize the overall effects of PZ-128. In particular, selected center(s) will participate in a sub-study that will include specific testing to assess inhibition of platelet aggregation and the pharmacokinetic/pharmacodynamics (PK/PD) relationship of PZ-128.

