Normal study termination/discontinuation is defined as the completion of all visits and procedures listed under **Section 1.2**. Early study termination/discontinuation occurs if the subject fails to complete the entire study, through to the 90-day telephone follow-up. Early termination from the study may occur for the following reasons:

- Subjects are free to withdraw from the study at any time for any reason- formal withdrawal of the subject's consent to participate further in any of the remaining study procedures must be documented by the investigator/qualified designee;
- In the opinion of the investigator, the subject cannot safely perform the procedures required by the protocol (e.g., adverse event, concomitant treatment);
- Subject does not comply with the protocol instructions given by the investigator/qualified designee;
- The subject becomes pregnant (pregnancy will be followed as per **Section 6.7.2.2.7**);
- The sponsor, Tufts Medical Center may terminate the study for any reason;
- The study may be terminated at any time by the national or local regulatory authorities overseeing and/or funding the trial (e.g., FDA, NHLBI/NIH, or IRB).

A subject has the right to discontinue participation in the study at any time for any reason without prejudice to his/her future medical care by the investigator or at the institution. Withdrawal of partial consent means that the subject does not wish to receive the study drug any longer but is still willing to collaborate in providing further data by continuing on study (e.g., participate in subsequent study visits/contacts or procedures, allow release of follow-up

information). Withdrawal of full consent means that the subject does not wish to receive further study drug and does not wish to or is unable to continue further study participation; subject data up to withdrawal of consent will be included in the subjects' study data. Withdrawal of partial or full consent by the subject must be documented in writing by the investigator/qualified designee. The investigator will discuss with the subject appropriate procedures for withdrawal from the study drug and/or study. Should a subject request or decide to withdraw from the study, all efforts will be made to complete and report the observations as thoroughly as possible up to the date of withdrawal. All information should be reported on the applicable eCRFs and the Sponsor should be notified promptly.

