6.5 Study Schedule

An overview of the study is provided in the Study Design Diagram in **Section 1.1** and the schedule of assessments/events is shown in the Study Flow Chart in **Section 1.2**. See **Section 6.6** for specific information on processes. Figure 1 provides a treatment and follow-up schema.

The sponsor has specified a schedule of intervals relative to the day of randomized treatment for the return visit to the clinic and the telephone contacts, with a "window" of days around each visit/contact. The sponsor strongly requests that the subjects return for clinical visits or undergo telephone contacts as close to the specified interval as possible, and preferable within the defined window. If it is not possible for the subject to return within the visit "window", then the visit should be scheduled as close to the interval as is convenient for the subject and clinical site. Note that these are regularly scheduled visits/time points; if an unscheduled visit is required by the investigator or sponsor because of clinical circumstances or other unforeseen event, this will be allowed. All other aspects of care beyond those specified in the protocol will be based on the judgment and discretion of the investigator. All data collected will be used in the conduct of the study.

Figure 1. Study and Treatment Schema

*Specific P2Y₁₂ inhibitor drugs and doses will be administered as per the investigator’s discretion/standard of care (e.g., clopidogrel, prasugrel or ticagrelor)

ASA=aspirin; IP=investigational product; LMH=low molecular weight heparin; UFH=unfractionated heparin

Each subject randomized in this trial will participate for approximately 15 weeks, including a screening period of up to 14 days prior to the administration of the study drug and cardiac catheterization, the hospitalization phase, and a 90-day follow-up phase after the study drug administration as follows:

- Screening/Enrollment Period: up to 14 days prior to cardiac catheterization/PCI and study drug administration
- Hospitalization Phase: inpatient or outpatient period of hospitalization for care associated with the study drug administration and cardiac catheterization ± PCI through discharge
- Outpatient follow-up visit: 14 days (± 5 d) post study drug administration
- Telephone follow-up contact: 30 days (± 5 d) post study drug administration
- Telephone follow-up contact: 90 days (± 7 d) post study drug administration

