7.2 General Aspects of Statistical Evaluation

Statistical analyses will be performed using SAS version 9.23 and, where appropriate (e.g., specific pharmacokinetic analyses) other validated software. Statistical analyses will be performed in accordance with the study protocol, and a comprehensive Statistical Analysis Plan (SAP) which will be prepared before unmasking of the data. The SAP will provide further details of the analyses and presentation of the data and will contain ground rules and data handling conventions used to perform the analyses. Both the data and the proposed methods of analyses will be reviewed continuously during the study by the study team, which includes input from statistical, clinical and data management personnel. Before database lock, a masked review will take place during which all important protocol deviations will be discussed and agreed by the team and any ambiguities in study outcomes will be adjudicated in a masked fashion by the protocol team.

The primary and secondary outcome measures will be treated as binary outcomes with any individual experiencing the event within the specified time frame after treatment classified as

positive for the outcome and other individuals classified as negative. Details of the measures will be included in the SAP.

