7.3 Data Sets

Safety analysis set

Safety evaluations will include subjects who have been randomized and who have received any amount of study drug treatment. Subjects will be evaluated according to treatment actually received. The safety analysis set will be used as the primary analysis dataset for the reporting of both the primary and secondary safety analyses as described below.

Intention-to-treat analysis set

Efficacy analyses will be carried out on an intent-to-treat basis, and all evaluations will include all subjects who receive randomization assignment, irrespective of initiation of treatment, who provide at least one outcome assessment. Subjects will be analyzed according to the assigned study treatment irrespective of any treatment allocation errors.

Per-protocol analysis sets

Per-protocol analysis sets will also be defined during the masked review for total bleeding events, and key efficacy outcome measures. Subjects will be excluded from the per protocol analysis sets as a result of protocol deviations likely to influence the outcome variables (exact details of possible protocol deviations will be detailed in the SAP). Similar conclusions from both the safety analysis set and per protocol analysis set are required for a robust interpretation of the bleeding event results.

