7.6.2 Methodology

The proposed phase 2 study is not of sufficient size or of sufficient follow-up duration to allow analysis of clinical event rates.

Two alternative approaches will be used to evaluate the differences in risk of the various secondary outcome measures. The first will utilize generalized linear models analogous to those used for the safety outcomes. In addition because each of these outcome measures can be evaluated using a time to event approach, survival analyses will be used to examine those outcomes. Kaplan-Meier estimates of the cumulative risk of each outcome will be calculated to investigate differences between the treatment groups in the time to occurrence, and a Cox Proportional hazard model that accounts for the risk stratification variables described above will be used to assess risk differences in the 3 treatment groups. All of these analyses will be interpreted descriptively, with no adjustment for multiple comparisons. We anticipate that some analyses will be conducted for specific subgroups (e.g., influence of baseline risk factors, concomitant therapies), but these subgroup analyses will again be considered exploratory and treated as descriptive analyses. Details will be provided in the SAP. Generalized linear models comparable to those used for the safety outcomes will also be used to evaluate the effect of investigator choice of P2Y₁₂ inhibitor on each of the MACE components.

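### Section 6.5.11 stops entry of non-serious bleeding at a call that may come on day 25, although the primary endpoint runs to day 30; treated subjects lost before day 30 also count as bleed-free

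*Combined protocol and SAP*

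**What the plan says.** **Capture of bleeding.** Section 6.7.1.1 defines the primary endpoint over 30 days. Sections 6.6.1, 6.7.2.2 and 7.5.4 run adverse-event capture, bleeding included, over the same 30 days. Section 6.5.11 instead ends eCRF entry of non-serious events, bleeding included, at the 30-day contact. Section 6.5 gives that contact a window: "Telephone follow-up contact: 30 days (± 5 d) post study drug administration". Section 6.1 gives the same window. Serious events are collected to the 90-day call.

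**Scoring.** Section 7.2 treats the outcomes as binary. Anyone with the event in the time frame is "positive for the outcome and other individuals classified as negative". The primary analysis set has no follow-up condition (Section 7.3): "Safety evaluations will include subjects who have been randomized and who have received any amount of study drug treatment". Section 7.5 admits only adjudicated bleeding.

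**Incomplete follow-up.** On full withdrawal of consent, "subject data up to withdrawal of consent will be included" (Section 6.3.3). A per-protocol set for bleeding is planned (Section 7.3): "Subjects will be excluded from the per protocol analysis sets as a result of protocol deviations likely to influence the outcome variables". Its deviation list is left to the SAP, as are data-handling conventions (Section 7.2). Section 7.6.2, on efficacy, says that "because each of these outcome measures can be evaluated using a time to event approach, survival analyses will be used to examine those outcomes". In the Synopsis, the influence of baseline risk factors and concomitant therapies on the endpoints "will also be explored using generalized linear models and survival models".

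**The concern.** Two features can turn a primary-endpoint bleed into a non-event.

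1. A site that follows Section 6.5.11 and calls on day 25 may learn at the 90-day call of a day-27 bleed and leave it out of the eCRF. Sections 6.6.1, 6.7.2.2 and 7.5.4 would require the same bleed to be entered. The instructions conflict for the endpoint on which the trial's safety conclusion rests.
2. A treated subject who leaves on day 3 with no recorded bleed counts as bleed-free for 30 days.

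In a non-inferiority comparison of a risk difference, missed events can pull the estimate toward zero. Events are few, so single bleeds matter. With 16/400 against 8/200 the one-sided 95% Wald upper limit is 2.79%. With 20/400 against 8/200 it is 3.90%, or about 0.28 point per bleed.

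**Working it through.** **Inputs.** From Section 7.7: 400 PZ-128, 200 placebo, placebo risk 2-6% (4% used here), and tabled margins of 3.7% (true difference 0) and 5.9% (true difference 2%) at placebo 4%. From Section 7.5.4: a one-sided 95% limit. The documents give no loss rate and no distribution of bleeding over time, so those inputs are assumptions, shown as ranges.

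**The plan's own margins.** Margin = d + (1.645 + 0.842) × √[pT(1−pT)/400 + pC(1−pC)/200].
- d = 0: 2.487 × √(0.000096 + 0.000192) = 4.22%, against 3.7% tabled.
- d = 2%: 2% + 2.487 × √(0.000141 + 0.000192) = 6.54%, against 5.9% tabled.

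The tabled values do not reproduce at 80% power; at those margins power is about 70% and 69%. That is a separate matter. They serve below only as reference points, since Section 7.5.4 fixes no decision margin.

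**Step 1: the day 25-30 gap.** Expected bleeds in the trial:
- 4% in both arms: 600 × 0.04 = 24.
- PZ-128 at 7.7% (4% + 3.7%): 400 × 0.077 + 200 × 0.04 = 38.8.
- PZ-128 at 9.9% (4% + 5.9%): 400 × 0.099 + 200 × 0.04 = 47.6.

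Suppose 10-20% of bleeds fall evenly over days 2-30, a span of 28 days. Bleeds in the gap = total × share × 5/28:
- 24: 0.43 to 0.86.
- 38.8: 0.69 to 1.39.
- 47.6: 0.85 to 1.70.

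Given the late share, these are upper bounds: every call is on day 25 and every bleed in the gap is non-serious.

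**Step 2: subjects lost before day 30.** L is the share lost and f the share of lost subjects' bleeds that fall after loss. The true PZ-128 excess is set equal to the margin M. False non-inferiority is the exact binomial probability that the Wald upper limit lies below M.

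*Excess missed in proportion, equal loss:* observed risk = true risk × (1 − L × f) in each arm.

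| Loss per arm | f | M = 3.7% | M = 5.9% |
|---|---|---|---|
| none | – | 4.38% | 4.52% |
| 2% | 10-20% | 4.41-4.45% | 4.58-4.63% |
| 5% | 10-20% | 4.47-4.56% | 4.66-4.81% |
| 10% | 10-20% | 4.56-4.76% | 4.81-5.12% |
| 5% | 100% | 5.40% | 6.16% |
| 10% | 50-100% | 5.40-6.65% | 6.16-8.37% |

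*Excess entirely early:* observed PZ-128 risk = M + 4% × (1 − L × f); placebo = 4% × (1 − L × f).
- 10% loss in both arms, any f: 4.38-4.39% and 4.52-4.55%, in effect unchanged.
- 10% loss on PZ-128, 5% on placebo, f = 100%: 5.49% and 5.59%.

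*Loss on placebo only:* 10%, f = 100%: 2.72% and 2.91%, so the error moves the other way.

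**Step 3: expected missed PZ-128 bleeds at 10% loss.** 400 × 0.10 = 40 subjects; missed = 40 × risk × f, with f = 10-20%.
- Risk 4%: 0.16 to 0.32.
- Risk 7.7%: 0.31 to 0.62.
- Risk 9.9%: 0.40 to 0.79.

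**The case against.** **The gap is very narrow.** This stands. Calls made on or after day 30 leave no gap, and Section 6.5 asks for contacts close to the target day. Serious bleeding, including bleeding that leads to admission, is collected to day 90. TIMI minor bleeding needs a measured haemoglobin or haematocrit fall, and the flow chart in Section 1.2 schedules no haematology after the 14-day visit, so a qualifying late bleed needs unscheduled testing. The 90-day call still asks about bleeding and source documents. None of this tells the site to enter the event.

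**Missing-outcome handling belongs to the SAP.** This largely stands. Section 7.2 defers conventions and provides a masked review of ambiguities, and Section 7.3 requires similar conclusions from the per-protocol set. Partial withdrawal continues follow-up (Section 6.3.3), and Section 6.6 asks for final information after discontinuation. A reader might infer that the plan has no safeguard at all, but silence here does not show what the later SAP contains. What remains is that the protocol itself fixes the negative classification, and the per-protocol text does not name incomplete follow-up.

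**A proposed censored analysis has its own assumption.** Correct. It needs non-informative censoring, so it does not settle the case of differential loss.

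**Conclusion.** The conflict between Section 6.5.11 and the 30-day capture rules is real and needs reconciling whatever its size. On the assumed late share, it puts at most about 0.4-1.7 bleeds at risk. The scoring of lost subjects is the weaker, secondary point.

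Three stronger readings are tempting and not supported:
- *That the rules bias the trial toward non-inferiority.* Direction depends on when bleeds occur and which arm loses more subjects. With an early excess and equal loss the error rate does not change, and with more loss on placebo it falls.
- *That inflation needs 10% loss.* It does not: 5% loss with f = 100% already gives 5.4-6.2%.
- *That the effect must be negligible because bleeding is mainly periprocedural.* No section states this. Section 6.7.2.2 attributes expected bleeding to the procedure and to the background drugs, and the latter may continue after discharge.

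Low priority. All error rates assume placebo risk 4% and a true excess equal to a tabled margin that is not a decision margin.

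**What to change.** 1. **Reconcile Section 6.5.11 with Sections 6.6.1, 6.7.2.2 and 7.5.4.** Any bleed with onset on or before day 30 is entered in the eCRF and sent for adjudication at whatever contact it is reported, including the 90-day call. This is one changed sentence and slightly more data entry. No visit window has to change.
2. **Keep the planned binomial risk-difference model and the Section 7.2 classification as primary.** Report by arm the number of subjects without complete 30-day follow-up and their day of last contact.
3. **Add one sensitivity analysis** to Section 7.2 or the SAP: the 30-day risk difference with its upper one-sided 95% limit, from cumulative incidence with censoring at last contact and death as a competing event. State that it assumes non-informative censoring. A tipping-point analysis would cover differential loss. The cost is one table, a little analysis time and a slightly wider sensitivity interval.

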7.3 Data Sets

Safety analysis set

Safety evaluations will include subjects who have been randomized and who have received any amount of study drug treatment. Subjects will be evaluated according to treatment actually received. The safety analysis set will be used as the primary analysis dataset for the reporting of both the primary and secondary safety analyses as described below.

Intention-to-treat analysis set

Efficacy analyses will be carried out on an intent-to-treat basis, and all evaluations will include all subjects who receive randomization assignment, irrespective of initiation of treatment, who provide at least one outcome assessment. Subjects will be analyzed according to the assigned study treatment irrespective of any treatment allocation errors.

Per-protocol analysis sets

Per-protocol analysis sets will also be defined during the masked review for total bleeding events, and key efficacy outcome measures. Subjects will be excluded from the per protocol analysis sets as a result of protocol deviations likely to influence the outcome variables (exact details of possible protocol deviations will be detailed in the SAP). Similar conclusions from both the safety analysis set and per protocol analysis set are required for a robust interpretation of the bleeding event results.

7.4 Demographic and Other Baseline Characteristics

Demographic variables (e.g., sex, race, age, weight) and baseline clinical characteristics will be summarized by treatment group to assess comparability of treatment groups. No formal statistical analyses of these data comparing treatment arms are planned.

7.5 Safety Analyses

All safety endpoints for bleeding are defined in **Appendix B**. Only bleeding events adjudicated by the Clinical Events Committee (CEC) will be used in the primary and secondary analyses.

7.5.1 Primary Endpoint

The overall objective of this study is to evaluate the safety of two dose levels of PZ-128 compared to placebo. The outcome used to assess the safety of PZ-128 will be the incidence of major and minor bleeding events, as assessed by the TIMI system of classification, when PZ-128 or placebo is added to the standard of care (dual anti-platelet therapy with aspirin and P2Y₁₂ inhibitor) in subjects undergoing non-emergent PCI or non-emergent cardiac catheterization with the intent to perform PCI.

The primary safety outcome variable is the incidence of TIMI major plus minor bleeding not related to CABG through 30 days after treatment.

7.5.2 Secondary Safety Endpoints

The secondary safety outcome variables will be the following:

- incidence of bleeding that does not meet the TIMI criteria for major or minor (i.e., minimal bleeding) through 30 days after treatment;
- incidence of “clinically significant” bleeding through 30 days after treatment (TIMI major or minor or bleeding requiring medical attention);
- incidence of TIMI bleeding related to CABG through 30 days after treatment;

7.5.3 Exploratory Safety Endpoints

The following exploratory safety endpoint is not part of the objectives of the trial and is included as an additional way to evaluate bleeding for future consideration:

- incidence of bleeding events according to the BARC (Bleeding Academic Research Consortium) classification through 30 days after treatment.

